9.2 Statistical analysis plan

9.2.1 General principles of the statistical analysis

Statistical analysis will be conducted by a qualified statistician.

It should include:

- description of the volunteers enrolled to the study;
- number of volunteers who discontinued the study early;
- number of adverse events;
- efficacy analysis in groups;
- efficacy analysis in subgroups of volunteers;
- tolerability and safety analysis;
- statistical conclusions.

9.2.2 Description of volunteers at baseline

Give a description of the groups by age, gender, features of the diagnosis, medical history and efficacy and safety parameters.

To do this, one should use the descriptive statistics methods (for quantitative variables: n , arithmetic mean, median, standard deviation, minimum and maximum value; for categorical variables – frequency and proportion in %).

Assess 95 % confidence intervals for all parameters.

9.2.3 Efficacy analysis

Efficacy analysis based on quantitative variables

For each quantitative parameter, estimate its relative change after the exposure of the headset in comparison with the values before its exposure in % compared with the baseline using the following formula:

$$X(\%) = \frac{T_{\text{нiсiя}} - T_{\text{до}}}{T_{\text{до}}} \times 100\% \quad (3).$$

Give descriptive statistics values (n, arithmetic mean, median, standard deviation, minimum and maximum value) for each time point, grouping the data separately for each headset, and, also, show the difference between these indicators for each headset (“after” – “before”), and between the headsets (“VR headset A” – “VR headset B”). Present changes of the parameters over time graphically.

To analyse the efficacy of the four-factor dispersion analysis (ANOVA) based on the mixed model: the “exposure sequence” factors (levels “A – B” and “B – A”, “exposure period” (levels: “Period 1” and “Period 2” and “headset” (levels: “VR headset A” and “VR headset B”) are fixed, the “subjects” factor is random, distributed in the “exposure sequence” factor followed by the use of contrast analysis between the levels of the “headset” factor (level “VR headset B” – reference).

Check the normal distribution of the ANOVA residues using the Shapiro-Wilk test. In case the residues are not distributed normally, perform the ANOVA on ranks [19].

Efficacy analysis based on categorical variables

Calculate the descriptive statistics parameters (frequency and proportion in percentage).

Present results graphically.

To compare the proportions for the “VR headset A” and the “VR headset B” McNemar’s test should be used. In case the categorical variable has more than two categories, the marginal frequency test should be used.

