7. EFFICACY EVALUATION

7.1. Efficacy parameters

Principal and secondary parameters to be determined during the study:

Primary variable:

- Change in HF component after 5-minute exposure to the VR audio-visual sequence;

Secondary variables:

- Change in rMSSD after 5-minute exposure to the VR audio-visual sequence;
- Change in LF/HF ratio after 5-minute exposure to the VR audio-visual sequence;
- Change in SDNN after 5-minute exposure to the VR audio-visual sequence;
- Change in TP after 5-minute exposure to the VR audio-visual sequence;
- Change in HR after 5-minute exposure to the VR audio-visual sequence;
- Change in BP after 5-minute exposure to the VR audio-visual sequence;
- Change in Spielberger State-Trait Anxiety Inventory (STAI) score after 5-minute exposure to the VR audio-visual sequence.

The criterion for the prevailing efficiency for each variable is the presence of statistically significant differences between groups in favour of any of the groups with a directivity, which indicates the effectiveness of the technology. Procedures and methods required for efficacy evaluation are described in Section 4.13. The time and events schedule is shown in Section 4.12.

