9. STATISTICS

9.1 Justification of the sample size

The required sample size is the minimum sufficient number of subjects to obtain clinically and statistically significant outcomes of the clinical trial. Depending on the type of clinical trial and its design, as well as the types of variables used to evaluate the treatment effect, the sample size may vary.

The sample size depends on the following parameters:

- The size of the clinically significant differences (δ);
- Limiting probability of type I error α (usually for the tests of the prevailing efficiency is equal to 0.05 or 5% (two-tail));
- Limiting probability of type II error β (usually equal to 0.2) and, respectively, the power (80 %);
- Estimated on the basis of previous studies of intrasubject variability.

This study is designed to prove the superiority of the use of VR headset A vs. the use of the VR headset B for the main variable — “Change in HFcomponent after 5-minute exposure to the audio and visual VR sequence”.

To estimate the sample size, it is assumed that the following statistical hypotheses are verified for the demonstration of superiority under conditions of the single-group design:

$$H_0: \varepsilon \leq \delta \text{ vs. } H_a: \varepsilon > \delta, \quad (1)$$

where δ — the limit of superiority — the marginal value of the clinically significant differences in which it can be assumed that the investigational device (VR headset A) is superior to the comparable device (VR headset B);

$$\varepsilon = \mu_A - \mu_B \quad (2)$$

true difference between the arithmetic mean of the results obtained using the VR headset A and the VR headset B.

According to Chow et al [18], the sample size can be estimated using the following expression:

$$n = \frac{(z_{\alpha} + z_{\beta})^2 \sigma_m^2}{2(\varepsilon - \delta)^2} \quad (3)$$

where d — the size of clinically important differences as determined by experts; a — limiting probability of type I error (significance level), which in most cases is equal to 0.05 (5%); b — limiting probability of type II error; s_m — coefficient of variation, which is evaluated based on the results of previous studies.

In this study, the size of the clinically important differences d is 0.1 (10%), $a = 0.05$ (two-tailed), $b = 0.05$ (study power of 95 %). It is assumed that the difference e will be 0.25 (25 %), and s_m will be 0.35 (35 %). The results of calculations are given in the table below:

Statistical parameter	Value

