a — limiting probability of type I error	0.05
b — limiting probability of type II error	0.05
Percentage point of the standardized normal distribution for a	1.96
Percentage point of the standardized normal distribution for b	1.64
Difference in means e	0.25
The value of clinically significant differences d	0.1
Intrasubject variability s_m	0.35
Estimated sample size	36

Thus, it is necessary to enrol 36 volunteers to this study, according to the calculations. Yet, given that a large proportion of volunteers may not meet the inclusion criteria or non-inclusion criteria, and are the non-responders, at least 80 volunteers should be enrolled to the study. Yet, since it is planned to conduct the study of the virtual reality effect separately for different groups of volunteers, it is recommended that approximately 160 volunteers are included to get 100 randomized volunteers.

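### The arithmetic mean of the percent change in 9.2.3 is positive when nothing has changed, so each headset's HF rise is overstated; a real difference between headsets is enlarged slightly.

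*Protocol*

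**What the plan says.** Protocol 9.2.3 opens the efficacy analysis with one rule for all quantitative measures: "For each quantitative parameter, estimate its relative change after the exposure of the headset in comparison with the values before its exposure in" per cent. The formula is X(%) = (after − before)/before × 100. The next instruction is: "Give descriptive statistics values (n, arithmetic mean, median, standard deviation, minimum and maximum value) for each time point, grouping the data separately for each headset". It also asks for the after-minus-before and A-minus-B differences.

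The comparison between headsets is a mixed-model crossover ANOVA "followed by the use of contrast analysis between the levels of the “headset” factor", with headset B as reference. The only provision against skewness is: "In case the residues are not distributed normally, perform the ANOVA on ranks". No log transformation or log ratio is named.

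Section 7.1 gives the primary variable as "Change in HF component after 5-minute exposure to the VR audio-visual sequence". Its secondary variables include "Change in LF/HF ratio after 5-minute exposure to the VR audio-visual sequence" as well as rMSSD, SDNN, total power and the STAI score. Section 9.1 states its inputs as percentages: an A−B difference of 25%, a superiority limit of 10%, and, in its table, "Intrasubject variability s_m 0.35". It describes the last of these as a coefficient of variation.

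**The concern.** HF, LF/HF, total power, rMSSD and SDNN are positive quantities measured with noise. Dividing by a single noisy value treats rises and falls unequally: a fall cannot exceed 100%, while a rise has no bound. Take two volunteers whose HF goes from 200 to 400 and from 400 to 200. They score +100% and −50%, an average of +25%, although the group as a whole has not moved.

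The primary objective concerns autonomic recovery, so the mean percent change after each headset is a figure that readers will look for. As defined, it shows some HF recovery under the active and the sham headset alike when there is none. The same mechanism raises LF/HF, so a parasympathetic marker and the ratio that should move against it can both appear to increase from noise alone.

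STAI has a separate difficulty with the same formula. With 20 items scored 1 to 4, its total starts at 20, so a percentage depends on an arbitrary origin. A 5-point fall is −5/25 = −20.0% from 25 but −5/44 = −11.4% from 44.

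**Working it through.** **The protocol's own figure.** With e = 0.25, d = 0.10, s_m = 0.35, z = 1.96 and 1.64 (9.1): n = (1.96 + 1.64)² × 0.35² / (2 × 0.15²) = 35.28, rounded up to 36. The stated sample size is reproduced. The protocol therefore carries its effect, limit and variability on a percent scale.

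**Formula for the bias.** Assume log-normal noise, since the protocol gives no distribution. Let R be the true after/before ratio and V the noise variance of ln(after/before). Then E[after/before] = R × exp(V/2), so with no change (R = 1) the mean of X(%) is 100 × (exp(V/2) − 1). The median of X(%) is 0%.

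**Size for HF with no change.** The protocol does not settle what 35% measures, so each reading is shown.

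| Reading of 35% | V | Mean X(%) |
|---|---|---|
| CV of each recording, independent errors: V = 2 ln(1 + 0.35²) | 0.2311 | +12.25% |
| CV of each recording, error correlation 0.5 | 0.1156 | +5.9% |
| CV of each recording, error correlation 0.75 | 0.0578 | +2.9% |
| SD of the percent change: exp(V/2) × √(exp(V) − 1) = 0.35 | 0.1047 | +5.4% |
| SD of the A−B difference: same equation, set to 0.35/√2 = 0.247 | 0.0563 | +2.9% |

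If each recording's CV were 50% with independent errors, the mean would be +25%.

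**LF/HF.** With LF and HF each at a CV of 35% and before and after errors independent, the mean under no change is 100 × (exp(2 × 0.1156 × (1 − r)) − 1), where r is the correlation of the LF and HF errors within a recording. It is +26% at r = 0, +12% at r = 0.5 and +6% at r = 0.75. The protocol gives no value for r.

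**A−B contrast, headsets equal.** Both headsets carry the same bias, so it cancels. In 20,000 simulated 2×2 crossovers (each recording's CV 35%, independent errors, period-adjusted t-test), the mean A−B was between −0.12 and +0.04 points and the rejection rate was 0.048 at both N = 36 and N = 100. With both headsets raising HF by a true 25%, A−B was about −0.1 and the rejection rate 0.047 to 0.049.

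**A−B contrast, headsets different.** The expected difference is (R_A − R_B) × exp(V/2). For a true 25 points this gives 25 × 1.0285 = 25.7 at the low end and 25 × 1.1225 = 28.1 at the high end. The simulation at the high end gave 28.1.

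**On the log-ratio scale.** No change averages 0% for each headset, and true responses of 1.25 and 1.00 give A/B = 1.25 at any noise level. At N = 100 in the noisiest case, power for that effect is about 0.90, against 0.87 on the percent scale.

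**The case against.** The strongest reply is that the trial is decided elsewhere. Sections 4.1, 7.1 and 9.1 make success a matter of the difference between headsets, and 9.2.3 tests it by a contrast. A reader might infer that noise alone creates or enlarges an A−B difference. It does not: with equal headsets the contrast centres on zero and keeps its 5% error rate. This part of the objection stands in full.

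It is also true that no sentence says X(%) is summarised by its mean or is the ANOVA response. The descriptive statistics are requested by time point, which can be read as raw values, and raw after-minus-before differences do not have this bias. The link is an inference from the order of the instructions and from the percent inputs of 9.1. It is a reasonable one, because otherwise the formula has no stated use. The median is requested too, and it is unaffected, but it is not named as the effect to be reported. The rank ANOVA is conditional on a normality test and changes only the comparison of headsets, not the per-headset percentages.

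Three stronger readings are tempting and not supported:

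- **The artefact exceeds the 10% limit.** That limit is an A−B margin, where the bias cancels if the headsets are equal, and +12% is the top of the range.
- **A false per-headset finding.** With 100 volunteers and no change, a 95% interval for a headset's mean X(%) would lie wholly above zero in roughly 20% to 57% of trials instead of 2.5%. But 9.2.3 requests no such interval or test; the confidence intervals in 9.2.2 belong to the baseline description.
- **LF/HF rises by 26% from noise.** That needs LF and HF from the same ECG to vary independently.

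Finally, transformations are often left to a separate analysis plan. Here, however, the protocol itself fixes the formula for every quantitative parameter.

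**Conclusion.** The point holds for the reported per-headset changes. Summarised by the arithmetic mean, the 9.2.3 formula shows an HF rise of about 3% to 12% under either headset when nothing has changed, and it pushes LF/HF upward too. The size rests on log-normal noise, on the protocol's 35%, on what that 35% measures and on the before–after error correlation; that the mean is applied to X(%) is inferred.

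The primary comparison is not undermined. Its type I error holds, and only a true difference is magnified, by 0.7 to 3.1 points on 25. This is a correction that should be made to the reported magnitudes. It is not a threat to the validity of the headset test.

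**What to change.** In 9.2.3, for HF, LF/HF, total power, rMSSD and SDNN, replace X(%) by ln(after/before). Use it for the per-headset summaries and as the response in the crossover ANOVA already specified. Report 100 × (exp(mean) − 1) with its 95% confidence interval for each headset, and the A/B ratio of changes with its 95% confidence interval. For STAI, report the change in points.

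Section 9.1 must be aligned, because it defines the effect as a difference of arithmetic means; state there that the 25%, 10% and 35% are read on the ratio (log) scale. As an illustration with the protocol's own expression, reading them as ratios of 1.25 and 1.10 and a CV of 35% gives ln 1.25 − ln 1.10 = 0.1278 and log-variance 0.1156. Then n = 3.60² × 0.1156 / (2 × 0.1278²) ≈ 45.8, or 46 instead of 36, well within the 100 to be randomised.

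No new data are needed. The cost is that effects are read as geometric-mean ratios and the reported percentages will be slightly smaller.

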9.2.4 Safety and tolerability analysis

Provide parameters of descriptive statistics used to assess the safety and tolerability of each individual headset.

Since the safety of the product will be evaluated based on the development (or lack thereof) of negative (undesired) adverse events and reactions, the parameters of descriptive statistics (frequency and rate as a percentage) should be provided. Evaluate serious AR/ADE and non-serious AR/ADE both together and separately.

9.2.5 Significance levels

The level of significance is equal to 0.01 for the Shapiro-Wilk test, and equal to 0.05 for other tests.

10. DIRECT ACCESS TO SOURCE DATA/DOCUMENTS

10.1. Data management

The CRF should be filled by 100 % and contain valid information. In case of availability of data, the validity of which is reasonably doubted, and it is impossible to check such data, they should be excluded from statistical processing.

All documentation related to the study, as well as information regarding the volunteers participating in it, is confidential. If necessary, the report and study documents will use only the identification numbers of the volunteers participating in the study.

10.2. CRF

Case Report Forms will be used in the study to collect information. Data from the paper CRF will be introduced by several CRO employees into an electronic data base, after which a comparison of data will be carried out to detect physical errors.

10.3. Source documentation

In this study, the CRF is considered to be the source documentation and is a confirmation of the reality of existence of a particular volunteer, and confirms the reliability of the collected/obtained data. The source documentation is filled in at the study site.

10.4. Corrections in source documentation

All entries in the source documentation (CRF) must be legible. In case of corrections, it is necessary to leave the previous values so that they are eligible. Each correction must be dated, the reasons for the correction explained, and must be verified with the signature of the person who made the correction.

10.5. Direct access to source documentation

For the purposes of ongoing inspections, the documentation for this study should be provided by the investigator and the Healthcare Facility (HCF) to the Ethics Committee at the Healthcare Facility, as well as persons authorized to carry out the audit and monitoring of the study.

11. QUALITY CONTROL AND ASSURANCE

The control over quality and completeness of data entry will be performed by the authorized representative of the CRO or the Sponsor during the monitoring visit.

A 100 % verification of signed Informed Consent Forms will be conducted. The quality control will be carried out by the qualified personnel, who will monitor the study on behalf of the CRO or the Sponsor.

The responsible investigator should provide free access to the CRF, virtual reality headsets, and study documentation (Investigator's personal file) for representatives of the Sponsor and the CRO. Also, the responsible investigator provides free access to all study documentation for monitoring and auditing.

The investigator is obligated to notify the participants of the study and to obtain their consent, according to which all personal information may be studied in the process of data verification within the framework of monitoring/audit conducted by the Sponsor, its authorized representatives, or may be subject to verification by the regulatory authorities. In this case, participation in the study and personal information will be considered as confidential, as it is established by the law, and not subject to disclosure. Audits and inspections are conducted to assess the compliance with the principles of the Good Clinical Practice, in accordance with the legislation of Ukraine in force and the Study Protocol.

Audits may be conducted by the Sponsor or a designated agent in accordance with its Standard Operating Procedures (SOPs) or according to the SOP of the Authorized Agent.

In the process of monitoring and clinical audit, the availability of the set of documents in the Investigator's File, the execution of the study in accordance with the Protocol, the filling of the CRF will be inspected. An audit or verification may include, for example, examination of all source documentation, distribution logs for virtual reality headsets, the CRF, some or all equipment used in the study.

Representatives of the Sponsor can conduct a number of visits to the SS. Prior to study initiation, monitors acting on behalf of the Sponsor may visit the SS to verify the suitability of the institution for conduction of the study, as well as to discuss responsibilities of investigator in the study. After successful procurement of all the necessary documentation (including autobiographies and supporting documents, signed agreements on conduction of clinical study, approval of the Protocol by the Ethics Committee at the HCF), the Sponsor will arrange for delivery of virtual reality headsets and other equipment to the study site.

The initial visit to the study site will be scheduled for a date agreed by both parties. The enrolment of volunteers is not allowed prior to the initiating visit to the study site, as well as before the staff of the study site obtains a written approval for the beginning of enrolment of volunteers. During the initiating visit to the study site, all employees who are likely to participate in the study should receive introductory information including, but not limited to (the list is not exhaustive), a review of the study protocol and the processes for obtaining informed consent, the general responsibilities of the study site staff, the questions for testing. Information about this visit will be documented in the report.

Throughout the study, the Sponsor will contact the study site staff on a regular basis. Study monitors will periodically visit the study site during the study to perform routine monitoring visits. The monitor will carry out audits to assess the accuracy, completeness, and relevance of the clinical and source documentation. The monitor will also check the proper protection of the rights of the study subjects, as well as provide an assessment of the compliance of the study procedures with the requirements of the Protocol, the requirements of the Good Clinical Practice, and all regulations.

As part of the data verification, it is assumed that all source documentation will be provided for verification to the Sponsor or its representatives/monitors.

In accordance with the current standard operating procedures (Sponsor's or its representative's) at the SS, the site closing visit will be conducted, during which the Sponsor or its representative will analyse all Informed Consent Forms, the CRF, and other documentation.

The Sponsor or its representative will meet the investigator or the study site staff during the closing visit to explain the documentation retention procedures, publication policies, the possibility of audits at

the site, and the disclosure of financial information. The investigator is obliged to inform the Ethics Committee at the HCF of the completion of the study.

The investigator must keep all documentation pertaining to this study in the archives of the institution for 15 years. Documentation is submitted to the archive once the study is over and the site is closed. The fact of the submission of documents to the archive by the Investigator should be documented by an appropriate act submitted to the Sponsor or the CRO.

12. REGULATORY, ETHICAL AND ADMINISTRATIVE RULES

12.1. Ethical principles

This study is conducted in accordance with the principles proclaimed at the 18th World Medical Association (Helsinki, 1964), last edited in 2013, the Guideline for Good Clinical Practice (GCP), as well as the legislative acts of Ukraine.

A copy of the letter of the Ethics Committee at the HCF with the approval of the Protocol should be given to the Sponsor to obtain consent to participation in this study from any volunteers.

This study will start only upon approval of the Clinical Study Protocol by the Ethics Committee at the HCF, where the study will take place.

In the course of the study, the Investigator should submit timely reports on the progress of the study to the Ethics Committee at the HCF. Copies of all communications and correspondence with the Ethics Committee at the HCF should be provided to the Sponsor. In addition, upon termination or early termination of the study, the investigator should submit a final report to the Ethics Committee at the HCF. A copy of the report will be provided to the Sponsor.

